9.7.1.8.1 EXTENT OF EXPOSURE

The number of cycles administered, duration of treatment, and the number of subjects requiring dose reductions, treatment interruption, treatment delay, and treatment discontinuation due to adverse events will be summarized.

9.7.1.8.2 ADVERSE EVENTS

The AE verbatim descriptions (investigator terms from the CRF) will be classified into standardized medical terminology using the Medical Dictionary for Regulatory Activities (MedDRA). Adverse events will be coded to the MedDRA (Version 20.0 or higher) lower level term (LLT) closest to the verbatim term. The linked MedDRA preferred term (PT) and primary system organ class (SOC) are also captured in the database.

A treatment-emergent adverse event (TEAE) is defined as an AE that emerges during treatment, having been absent at pretreatment or

- Reemerges during treatment, having been present at pretreatment (Baseline) but stopped before treatment, or
- Worsens in severity during treatment relative to the pretreatment state, when the AE is continuous.

Only those AEs that are treatment-emergent will be included in summary tables. All AEs, treatment-emergent or otherwise, will be presented in subject data listings.

The incidence of TEAEs will be reported as the number (percentage) of subjects with TEAEs by SOC and PT. A subject will be counted only once within an SOC and PT, even if the subject experienced more than 1 TEAE within a specific SOC and PT. The number (percentage) of subjects with TEAEs will also be summarized by highest CTCAE grade (CTCAE v5.0).

The number (percentage) of subjects with TEAEs will also be summarized by relationship to study drug (Yes [related] and No [not related]).

The number (percentage) of subjects with treatment-emergent serious adverse events (SAEs) will be summarized by MedDRA SOC and PT. A subject data listing of all SAEs will be provided.

The number (percentage) of subjects with TEAEs leading to death will be summarized by MedDRA SOC and PT. A subject data listing of all AEs leading to death will be provided.

The number (percentage) of subjects with TEAEs leading to discontinuation from study drug will be summarized by MedDRA SOC and PT. A subject data listing of all AEs leading to discontinuation from study drug will be provided.

9.7.1.8.3 LABORATORY VALUES

Laboratory results will be summarized using Système International (SI) units, as appropriate. Hematology and chemistry values and their changes from baseline will be summarized using descriptive statistics (mean, standard deviation, median, minimum, maximum). Shift from baseline to post-baseline CTCAE grade for hematology and chemistry tests will be presented.

Laboratory test results will be assigned a classification according to CTCAE grade ([Appendix 1](#)). Urinalysis data will be listed.

9.7.1.8.4 VITAL SIGNS

Descriptive statistics for vital signs parameters (ie, systolic and diastolic BP, pulse, temperature, weight, and height) and changes from baseline will be presented by visit.

9.7.1.8.5 ELECTROCARDIOGRAMS

ECG assessments will be performed. QT intervals will be measured from Lead II and will be corrected for heart rate (QTc) using Fridericia's (QTcF) and Bazett's (QTcB) correction factors. The primary QTc parameter will be QTcF. Secondary parameters will be QTcB, QT, QRS, and heart rate.

A shift table will be provided for baseline to post-baseline shift in ECG interpretation (categorized as normal; abnormal, not clinically significant; and abnormal, clinically significant).

In addition, the number (percentage) of subjects with at least 1 post-baseline abnormal ECG result in QTcF will be summarized. Clinically abnormal ECG results in QTcF will be categorized as follows:

Absolute QTc interval prolongation:

- QTc interval >450 ms
- QTc interval >480 ms
- QTc interval >500 ms

Change from baseline in QTc interval:

- QTc interval increases from baseline >30 ms
- QTc interval increases from baseline >60 ms

9.7.1.8.6 OTHER SAFETY ANALYSES

Karnofsky and Lansky performance status scores will be summarized descriptively.

9.7.2 Determination of Sample Size

For the first line therapy in pediatric patients with NRSTS, RMS, or EWS, the literature indicated that the ORR (complete or partial response) ranged from 33.3% to 63% (Pappo, et al., 1997; Sandler, et al., 2001). In children or patients with refractory solid tumor or rhabdomyosarcoma, the ORR of a treatment ranged from 0 to 50% (Jacobs, et al., 2010; Mascarenhas, et al., 2010). At the time of the design of this study, there was limited data available for eribulin and irinotecan as a treatment in the target populations.

Phase 1: Up to 6 subjects can be enrolled into each dose level, there are 2 schedules being evaluated (Schedule A and Schedule B). Therefore, a maximum of 36 subjects (not including subjects <12 months) are anticipated to be enrolled on this phase. Note: Subjects <12 months will not contribute to the determination of MTD/RP2D and data is for descriptive purposes only.

Phase 2: A total of approximately 75 subjects (approximately 25 in each histology group) will be enrolled. A Simon two-stage design will be used for each histology group. The following hypothesis will be tested at a one-sided 5% significance level:

$$H_0: p \leq 30\% \quad \text{Vs} \quad H_a: p \geq 55\%.$$

In the first stage, 9 subjects will be accrued. If there are 2 or fewer responses in these 9 subjects, the enrollment to this histology type (RMS, NRSTS and EWS) will be stopped. Otherwise, approximately 16 additional subjects will be enrolled in the second stage for a total of approximately 25 subjects per histology. The null hypothesis will be rejected if 12 or

more responses are observed in 25 subjects. This design yields a type I error rate of 0.05 (one-sided) and power of 80% when the true response rate is 55%.

Note: Subjects aged >6 to <12 months and subjects ≥ 18 to ≤ 25 years will be included for descriptive purposes only and will not contribute to the full sample size analyses for this study. As subjects in the age group >6 months to <12 months will receive approximately 75% of the RP2D of eribulin (rationale for lower dose is provided in Section 9.4.4 of the protocol) and the EMA PDCO requested that subjects in the age group ≥ 18 to ≤ 25 years old should not be included in the full sample size analyses.

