All subjects will have an off-treatment visit within 28 days after the last dose of study medication. After discontinuation from study treatment and completing the off-treatment visit, subjects will be followed up at least 4 weeks later (ie, greater than or equal to 28 days after last dose, but no more than 1 year) unless they withdraw consent.

Subjects who discontinue without objective evidence of disease progression will continue to have tumor assessments performed as per the Schedule of Assessments until disease progression, death, or another anticancer therapy is initiated, whichever occurs first, unless study is terminated. Follow-up data will be required unless consent is withdrawn.

Number of Subjects

The maximum number of subjects is approximately 111 (not including subjects of age <12 months).

Up to 36 subjects in Phase 1 and a total of approximately 75 subjects in Phase 2.

For Phase 2, Simon's two-stage design will be used. Nine subjects will be enrolled on to each histology type (RMS, NRSTS and EWS) in the first stage, at which point a futility analysis will be performed. Enrollment will be terminated if 2 or fewer responses are observed in these 9 subjects. If more than 2 responses are observed, then enrollment will continue to approximately 25 subjects in each histology type.

Inclusion Criteria

Subjects must meet all of the following criteria to be included in this study:

1. Age:

- a. ≥ 12 months to ≤ 25 years at the time of consent (no more than 25% of subjects between the ages of 18 and 25 years will be enrolled in this study).
- b. In Phase 1, >6 months and <12 months at the time of consent (Schedule A only) subjects will be enrolled one dose level behind the ≥ 12 months subjects in order to maximize safety for infant subjects. In Phase 2, subjects aged >6 months and <12 months at the time of consent will be enrolled to Schedule A with a modified dose of eribulin, Dose Level -2 (0.8 mg/m^2 Day 1 and Day 8) with the irinotecan dose maintained (40 mg/m^2 Day 1 – Day 5) of a 21-day cycle in order to maximize safety for infant subjects.

2. Diagnosis:

Phase 1: Histologically confirmed solid tumor, excluding CNS tumors, which is relapsed or refractory, and for which there are no currently available therapies.

Phase 2: Histologically confirmed RMS, NRSTS and EWS which is relapsed or refractory having received at least 1 prior systemic therapy, including primary treatment.

3. Disease status:

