Eribulin, irinotecan and its active metabolite, SN-38 will be analyzed using validated liquid chromatography with tandem mass spectrometry (LC-MS/MS) methods.

Statistical Methods

Primary Endpoints

- Phase 1: The MTD/RP2D of eribulin mesilate in combination with irinotecan hydrochloride in pediatric subjects with relapsed/refractory solid tumors, excluding CNS tumors
- Phase 2: Objective response rate (ORR): defined as the proportion of subjects achieving a best overall response of confirmed partial or complete response, as determined by investigator review.

Secondary Endpoints

Phase 1 & 2:

- Safety and tolerability: adverse events (AEs), serious adverse events, clinical laboratory values, ECG parameters, vital sign measurements and physical examinations
- The pharmacokinetic profile of eribulin, irinotecan and its active metabolite

Phase 2:

- Progression-free survival (PFS): defined as the time from the first dose date to the date of disease progression as determined by investigator review, or death
- The Clinical Benefit Rate (CBR): defined as the proportion of subjects with best overall response (BOR) of CR, PR or durable SD based on RECIST 1.1 (durable SD >11 weeks)

Subjects aged >6 to <12 months and subjects ≥ 18 to ≤ 25 years will be included for descriptive purposes only and will not contribute to the full sample size analyses for this study. As subjects in the age group > 6 months to <12 months will receive approximately 75% of the RP2D of eribulin (rationale for lower dose is provided in Section 9.4.4 of the protocol) and the EMA PDCO requested that subjects in the age group ≥ 18 to ≤ 25 years old should not be included in the full sample size analyses.

Analysis Sets

Full Analysis Set (FAS) will consist of subjects who receive at least 1 dose of either study drug.

Safety Analysis Set will consist of subjects who receive at least 1 dose of either study drug.

Pharmacokinetic Analysis Set (PAS) will include subjects who documented dosing history and at least one post-dosing quantifiable drug concentration.

Dose Evaluable Set (DES) for Phase 1 will consist of all subjects who completed Cycle 1 treatment and were evaluated for DLT, and those who discontinued during Cycle 1 due to DLT. The DES will be used for evaluation of each dose level for dose-escalation.

Dose escalation (Phase 1)

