The number of subjects with DLTs will be summarized for each dose level in each schedule being evaluated. The incidence of adverse events will also be summarized for each dose level, by preferred term and body system. Laboratory data and other safety assessments, such as vital signs, ECG, will be summarized for each dose level.

Primary Efficacy Analysis (Phase 2)

Efficacy analyses will be performed on the FAS. Antitumor activity of eribulin mesilate in combination with irinotecan hydrochloride will be assessed by ORR, defined as the proportion of subjects with best response designation of CR or PR as per RECIST 1.1, during treatment, divided by the number of subjects in the FAS.

ORR will be estimated and summarized for each histology type. A Simon two-stage design will be used within each histology type. The following hypothesis will be tested at a one-sided 5% significance level:

$$H_0: p \leq 30\% \quad \text{Vs} \quad H_a: p \geq 55\%.$$

The first stage will enroll 9 subjects. A futility analysis will be performed when the data for the 9 subjects is available (investigator assessed responses). If there are 2 or less responders among the 9 subjects, the enrollment in this histology type will be stopped. If there are 3 or more responders (CR or PR), the enrollment will continue to the second stage up to approximately 25 subjects. If there are 12 or more responders out of 25 subjects, the null hypothesis will be rejected. Collect and hold of tumor scans will enable a possibility to confirm responses in case independent review is required.

In addition, ORR along with respective confidence interval will also be provided by histology. Duration of response (DOR) will be calculated for responders and summarized descriptively. DOR is defined as the time from the first date of documented PR or CR to the date of disease progression or date of death (whichever occurs first).

Secondary Efficacy Analyses

PFS will be analyzed by Kaplan-Meier methodology and median PFS with 90% confidence interval will be presented.

Clinical benefit rate, defined as the proportion of subjects with best overall response (BOR) of CR, PR or durable SD based on RECIST 1.1, will be summarized descriptively. Durable SD is defined as SD with duration of more than 11 weeks.

Pharmacokinetic Analyses

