9.2 Discussion of Study Design

Study E7389-G000-213 is to be conducted as a multicenter, single arm study evaluating the safety and efficacy of eribulin mesilate in combination with irinotecan in children with refractory or recurrent solid tumors.

This study will follow on from Study E7389-A001-113, which has the primary aim of establishing the Maximum Tolerated Dose (MTD)/Recommended Phase 2 dose (RP2D) of eribulin mesilate in pediatric subjects with relapsed/refractory solid tumors, excluding CNS.

The aim of study E7389-G000-213 is two-fold:

Phase 1: To determine the MTD/Recommended Phase 2 Dose (RP2D) and optimal schedule of eribulin mesilate in combination with weekly or daily irinotecan hydrochloride in pediatric subjects with relapsed/refractory solid tumors, excluding, CNS.

Phase 2: To assess the objective response rate (ORR) and duration of response (DOR) of eribulin mesilate in combination with irinotecan hydrochloride in pediatric subjects with relapsed/refractory RMS, NRSTS and EWS.

The maximum number of subjects is approximately 111: Up to 36 subjects in Phase 1 and approximately 75 subjects in Phase 2. The sample size does not include subjects <12 months.

In Phase 1, eribulin mesilate will be administered as an intravenous (IV) infusion on Days 1 and 8 of each 21-day cycle at the dose determined by COG study ADVL1314 (Eisai Study E7389-A001-113), 1.4 mg/m², together with IV irinotecan hydrochloride administered in two different dose schedules:

Schedule A

- Irinotecan hydrochloride 20 mg/m² Days 1-5 of a 21-day cycle
- Irinotecan hydrochloride 40 mg/m² Days 1-5 of a 21-day cycle

Schedule B

- Irinotecan hydrochloride 100 mg/m² Day 1 and Day 8 of a 21-day cycle
- Irinotecan hydrochloride 125 mg/m² Day 1 and Day 8 of a 21-day cycle

These doses of irinotecan are derived from studies looking at the MTD of single agent irinotecan or irinotecan combinations administered at the various corresponding schedules (Blaney, et al., 2001; Vassal, et al., 2003; Casey, et al., 2009).

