9.3.1 Inclusion Criteria

Subjects must meet all of the following criteria to be included in this study:

1. Age:
 - a. ≥12 months to ≤25 years old at the time of consent (no more than 25% of subjects between the ages of 18 and 25 years will be enrolled in this study).
 - b. In Phase 1, >6 months and <12 months at the time of consent (Schedule A only) subjects will be enrolled one dose level behind the ≥12 months subjects in order to

maximize safety for infant subjects. In Phase 2, subjects aged >6 months and <12 months at the time of consent will be enrolled to Schedule A with a modified dose of eribulin Dose Level -2 (0.8 mg/m² D1 and D8) with the irinotecan dose maintained (Dose Level 1, 40 mg/m² D1 – D5) of a 21-day cycle in order to maximize safety for infant subjects.

2. Diagnosis:

Phase 1: Histologically confirmed solid tumors, excluding CNS tumor, which is relapsed or refractory, and for which there are no currently available therapies.

Phase 2: Histologically confirmed RMS, NRSTS or EWS which is relapsed or refractory having received at least 1 prior therapy, including primary treatment.

3. Disease status:

Phase 1: Subjects must have either measurable or evaluable disease as per RECIST 1.1.

Phase 2: Subjects must have measurable disease as per RECIST 1.1.

Measurable disease is defined as meeting the following criteria:

- a. At least 1 lesion of ≥ 1.0 cm in the longest diameter for a non-lymph node or ≥ 1.5 cm in the short-axis diameter for a lymph node that is serially measurable according to RECIST 1.1 using computed tomography/magnetic resonance imaging (CT/MRI).
- b. Lesions that have had radiotherapy must show subsequent radiographic evidence of increase in size by at least 20% to be deemed a target lesion.

4. Therapeutic options: Subject's current disease state must be one for which there is no known curative therapy.

5. Performance level: Performance score $\geq 50\%$ Karnofsky (for subjects >16 years of age) or Lansky (for subjects ≤ 16 years of age). Subjects who are unable to walk because of paralysis and/or previous surgeries, but who are in a wheelchair, will be considered ambulatory for the purpose of assessing the performance score.

6. Subjects must have fully recovered from the acute toxic effects of all prior anticancer treatments prior to study drug administration:

- Myelosuppressive chemotherapy: Must not have received within 21 days prior to study drug administration (42 days if prior nitrosourea).

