9.7.1.2 Definitions of Analysis Sets

Full Analysis Set (FAS) will consist of subjects who receive at least 1 dose of either study drug.

Safety Analysis Set will consist of subjects who receive at least 1 dose of either study drug.

Pharmacokinetic Analysis Set (PAS) will include subjects who have documented dosing history and at least one post-dosing quantifiable drug concentration.

Dose Evaluable Set (DES) for Phase 1 will consist of all subjects who completed Cycle 1 treatment and were evaluated for DLT, and those who discontinued during Cycle 1 due to DLT. DES will be used for evaluation of each dose level for dose-escalation and for determination of MTD.

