4 DETERMINATION OF SAMPLE SIZE

Phase 1: Up to 6 subjects can be enrolled in up to 3 dose levels, there are 2 schedules being evaluated (Schedule A and Schedule B). Therefore, a maximum of 36 subjects are anticipated to be enrolled on this phase (not including subjects <12 months). Note: Subjects <12 months will not contribute to the determination of MTD/RP2D and data is for descriptive purposes only.

Phase 2: Up to approximately 75 subjects (approximately 25 in each histology group) will be enrolled. Simon's two-stage design will be used for each histology group. The following hypothesis will be tested at a one-sided 5% significance level:

$$H_0: p \leq 30\% \quad \text{Vs} \quad H_a: p \geq 55\%.$$

In the first stage, 9 subjects will be accrued. If there are 2 or fewer responses in these 9 subjects, the enrollment to this histology type (RMS, NRSTS, and EWS) will be stopped. Otherwise, 16 additional subjects will be enrolled in the second stage for a total of 25 subjects. The null hypothesis will be rejected if 12 or more responses are observed in 25 subjects. This design yields a type I error rate of 0.05 (one-sided) and the power of 80% when the true response rate is 55%.

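### The protocol sets infants and 18–25-year-olds aside in Phase 2, but no analysis set does this, and the SAP as written counts every dosed subject in the 3-of-9 and 12-of-25 decisions

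*Protocol*

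**What the plan says.** **Protocol, on who counts.** Section 9.7.2 and the synopsis (Sample Size Rationale) give the Simon rule and then state that subjects aged >6 to <12 months and 18 to 25 years "will be included for descriptive purposes only and will not contribute to the full sample size analyses for this study". Two reasons are given: infants receive a lower eribulin dose, and the EMA PDCO asked that the 18–25 group "should not be included in the full sample size analyses". The term for the analyses they are kept out of is not defined.

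**Protocol, on the analysis.** Section 9.7.1.2: "Full Analysis Set (FAS) will consist of subjects who receive at least 1 dose of either study drug". The synopsis (Primary Efficacy Analysis) calculates ORR as responders "during treatment, divided by the number of subjects in the FAS" and then gives the decision rule. Sections 9.7.1.6.1 and 9.7.3 repeat the rule with no age condition.

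**Protocol, on numbers.** Section 9.2 gives a maximum of about 111 (36 in Phase 1, about 75 in Phase 2) and adds: "The sample size does not include subjects <12 months". It says nothing about ages 18 to 25. Section 9.3.1 caps that group: "no more than 25% of subjects between the ages of 18 and 25 years will be enrolled in this study".

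**SAP.** Section 4 repeats the Phase 2 design without the age note. The note it keeps concerns Phase 1: "Subjects <12 months will not contribute to the determination of MTD/RP2D and data is for descriptive purposes only". Sections 5.2.1 (analysis sets), 5.4 and 5.4.1 (primary efficacy) and 6 (futility) have no age limit. Section 5.3.4 plans no subgroup analyses. Ages 18 to 25 are not mentioned anywhere in the SAP.

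**The concern.** An exclusion placed straight after the sample size rule is most naturally read as an exclusion from the test. An exclusion that no analysis set, endpoint definition or decision rule carries out will not happen. An analyst working from the SAP would take the FAS, find every dosed subject in it, and apply 3 of 9 and 12 of 25 to all of them.

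A single responder can change either decision: 2 versus 3 of 9, or 11 versus 12 of 25. The trial is open-label with investigator-assessed response, so settling who counts once responses are known would be a data-driven choice.

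There is also a problem with the numbers. The headcount leaves out only subjects under 12 months, which implies that 18–25-year-olds are inside the approximately 25 per histology. If they are then removed from the test, fewer than 25 remain, and the plan gives no cut-off or power for that number.

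**Working it through.** **1. Inputs from the documents.** Null ORR 30%, alternative 55%, one-sided 5% (Protocol 9.7.2, SAP 4). Stage 1: 9 subjects, continue at 3 or more responses. Final: 25 subjects, reject at 12 or more. Cap on ages 18–25: 25%, study-wide (Protocol 9.3.1). The documents give neither the number of 18–25-year-olds nor any age-specific ORR, so steps 3 and 4 use assumed values shown as ranges.

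**2. The plan's own figures.** With X1 the stage 1 responses and X2 the stage 2 responses,

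P(reject) = Σ (x from 3 to 9) P(X1 = x) · P(X2 ≥ 12 − x), X1 ~ Bin(9, p), X2 ~ Bin(16, p).

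- p = 0.30: 0.0421
- p = 0.55: 0.8007

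This agrees with the stated 5% (as a nominal level) and 80%. A final bar of 11 would give 0.0898, so 12 is the right bar for 25 counted subjects.

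**3. Older subjects inside the 25 but excluded from the test.** The formula is the same, with n1 counted subjects in stage 1 and n in total. The stage 1 bar stays at 3, and the final bar is the smallest that keeps the error at or below 0.05. A 25% share of 25 is about 6.

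| Set aside | n1, n | Final bar | Error at 30% | Power at 55% |
|---|---|---|---|---|
| 6 of 25 | 7, 19 | 10 | 0.0291 | 0.6309 |
| 6 of 25 | 9, 19 | 10 | 0.0321 | 0.6668 |
| 3 of 25 | 8, 22 | 11 | 0.0359 | 0.7277 |
| 3 of 25 | 9, 22 | 11 | 0.0376 | 0.7442 |
| 2 of 25 | 8, 23 | 11 | 0.0493 | 0.7801 |
| 2 of 25 | 9, 23 | 12 | 0.0210 | 0.6792 |

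In the last row a bar of 11 gives 0.0521, just over the limit, so the bar moves to 12. If the bar of 12 (the only one stated) were kept throughout, power would be about 0.31 with 19 counted, 0.59 to 0.60 with 22, and 0.67 to 0.68 with 23.

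**4. Everyone pooled, as the SAP reads.** The bar is 12 of 25, the target-age ORR is 30% and the older-group ORR is q. The count in each stage is the sum of two binomials, combined by exact convolution. With 6 older, stage 1 is 7 + 2 and stage 2 is 12 + 4. With 2 older, they are 8 + 1 and 15 + 1.

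| q | P(reject), 6 of 25 older | P(reject), 2 of 25 older | Pooled ORR, 6 of 25 older |
|---|---|---|---|
| 20% | 0.0220 | 0.0341 | 0.276 |
| 30% | 0.0421 | 0.0421 | 0.300 |
| 40% | 0.0715 | 0.0507 | 0.324 |
| 55% | 0.1366 | 0.0650 | 0.360 |

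The last column is (19 × 0.30 + 6q)/25. These are false-positive rates for the target-age group. For the pooled population they are not type I errors when q exceeds 30%, because the pooled ORR is then above 30%.

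**5. Enrolment needed to keep 25 counted.** At a 25% share within a histology, 25/0.75 = 33.3. With 33 enrolled the older share is 8/33 = 24.2%; with 34 it is 9/34 = 26.5%. So up to 33 per histology, or 3 × 33 = 99 in Phase 2. For stage 1, 9/0.75 = 12.

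**The case against.** - **The SAP never says in words that these ages count.** Its rules refer to 9 and 25 subjects without naming an analysis set, and SAP 5.4 assigns the FAS to descriptive summaries. One could therefore say that the test population is undefined, not contrary to the protocol. But ORR is on the FAS, the FAS is everyone dosed, the rules carry no age limit, and the protocol synopsis puts the FAS denominator next to the Simon rule. Counting everyone is what following the text produces.
- **The headcount may be a leftover.** The wording on subjects under 12 months dates from Amendment 01, and 18–25-year-olds were admitted in Amendment 05. On the reading that the 9, 25 and 12 already mean contributing subjects only, 5% and 80% stand and what is missing is the total enrolment. This stands: the power loss in step 3 belongs to one of two readings, and the plan does not say which applies.
- **The sizes are hypothetical.** This stands too. Pooling moves the error rate only if ORR differs by age; at equal ORR it is exactly 0.042. Step 3 also depends on discreteness and on keeping the stage 1 bar at 3: a bar of 2 of 7 gives power 0.667 with 19 counted, and 2 of 8 gives 0.751 with 22.
- **An age flag may exist elsewhere.** Dataset specifications and table shells are separate documents (SAP 9 and 11). Even so, who counts in a stop/go decision and a hypothesis test belongs in the analysis-set definition.
- **Descriptive inclusion need not mean a subgroup table.** SAP 5.2.4 summarises age group at baseline and 5.4.1 lists response by subject. That is fair, but no efficacy summary for the set-aside ages is planned.

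**Conclusion.** The concern holds and must be fixed before the ORR rule is applied. The protocol sets two age groups aside from the Phase 2 test. Its own FAS does not do so, and the SAP omits the exclusion, so the population for the primary test differs between the protocol's note and the analysis that would be run.

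The stated design is correct for 25 counted subjects. The consequence elsewhere depends on the share of 18–25-year-olds and on their ORR, neither of which is given. Over 2 to 6 of 25 older subjects, pooling puts the chance of rejecting at a target-age ORR of 30% between 0.022 and 0.137, against 0.042 as designed. Excluding them from within 25 puts power between 0.63 and 0.78 with a re-derived final bar. Infants are outside the headcount, so they do not reduce the 25, but as the SAP stands their responses would still be counted.

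**What to change.** 1. In Protocol 9.7.1.2 and 9.7.1.6.1 and in SAP 5.2.1, 5.4.1 and 6, define the Phase 2 ORR test set as FAS subjects aged ≥12 months to <18 years at consent. Use it in place of the undefined term in Protocol 9.7.2.
2. State that the 9, the 25 and the 12 count only that set.
3. In SAP 5.3.4, plan separate descriptive summaries for the infants and for the 18–25-year-olds.
4. Say whether the approximately 25 per histology includes 18–25-year-olds, and choose one of two routes:
   - **Keep 25 target-age subjects.** This needs up to 33 enrolled per histology (about 99 in Phase 2) and up to 12 enrolled before stage 1 has 9 target-age subjects, so the recruitment pause must follow the target-age count. These figures assume the 25% cap holds within each histology. The cap is study-wide, so one histology could need more.
   - **Keep about 25 in total.** No subjects are added, but the cut-off and power must be restated for the target-age number attained, in place of 80%.

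Items 1 to 3 cost only wording. Item 4 costs either enrolment or a lower stated power.
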